2.2. Rationale for Study Design

This study design was chosen since the primary objective is to compare cumulative vasopressor

doses. Many patients that present with septic shock have multiple comorbidities necessitating chronic therapy with either β -blocker, ACE-Inhibitor, or both. Because little is known about the effects of chronic antihypertensives on vasopressor dosing and the severity of septic shock, a retrospective study was chosen.

2.3. Rationale for Dosage

Rationale for dosage is not applicable to this study because we will only be collecting pre-existing medical data with no prospective interventions and dosing is routine care.

3. CHARACTERISTICS OF THE RESEARCH POPULATION

3.1. Subject Characteristics

Number of Subjects:

It is estimated that approximately 200 patients will be included for this study. The individual number for each group will vary based on screening.

Gender and Age of Subjects:

No restrictions apply to gender of the study subjects. Only adult, non-pregnant patients will be included, defined as 18 years of age or older.

a) Racial and Ethnic Origin:

No restrictions apply to race or ethnic origin of the study subjects.

3.2. Inclusion and Exclusion Criteria

a) Inclusion Criteria:

- Adult patients 18 years of age or older
- Diagnosis of septic shock requiring vasopressor therapy (norepinephrine, epinephrine, phenylephrine, dopamine, or vasopressin)
- Admitted to the medical intensive care unit (MICU) at Rush University Medical Center (RUMC)
- Time frame: 01/01/2012 to 08/1/2016

b) Exclusion Criteria:

- Pregnant patients
- Transfer from outside hospital on vasopressors
- Admitted in cardiopulmonary arrest
- Prior arrest within 24 hours of admission to RUMC

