1. PURPOSE OF THE STUDY AND BACKGROUND

1.1. Hypothesis

- Chronic β -blocker or Angiotensin-Converting Enzyme (ACE)-inhibitor use is associated with decreased cumulative doses of vasopressors administered in the first 48 hours of septic shock

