1.2. Purpose of the study

- The primary objective is to determine the effect of chronic β -blocker or ACE-inhibitor on cumulative vasopressor dosing in the first 48 hours of septic shock.
- The secondary objectives of this study
 - To determine the effect of chronic β -blocker or ACE-inhibitor on cumulative vasopressor dosing in the first 6, 12, and 24 hours of septic shock.
 - To determine the effects of chronic β -blocker or ACE-inhibitor on:
 - Adequate fluid resuscitation
 - Cumulative inotrope use (48 hours)
 - Cumulative hydrocortisone use at 6, 12, 24, and 48 hours
 - To determine cumulative vasopressor dose of patients on chronic calcium channel blocker or other antihypertensives (clonidine, hydralazine, angiotensin-receptor-blocker (ARB))

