1.3. Background

Literature suggests that extended periods of tachycardia, in patients with shock, are associated with increased mortality.¹⁻⁴ Interventional trials have suggested that increased doses of catecholamines are associated with the increased mortality and the administration of esmolol infusions may improve survival in patients with shock requiring vasopressor agents.¹

What remains unknown is the effect of home exposure to antihypertensive therapies, specifically beta-blockers and ACE-inhibitor. This study will evaluate the effects of home antihypertensive therapy with beta-blockers and ACE-inhibitor on vasopressor dose administered within the first 48 hours of septic shock.

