4. SUBJECT IDENTIFICATION, RECRUITMENT AND CONSENT

4.1. Method Of Subject Identification And Recruitment

The study will be retrospective, and collected data will be a result of routine care. Adult patients 18 years of age or older with septic shock who received treatment with a vasopressor will be assessed for inclusion. Patients will be excluded if they are pregnant, transferred from outside hospital on vasopressor, admitted in cardiopulmonary arrest, prior arrest within 24 hours of admission to RUMC or if they required neuromuscular blockade.

Patients will be reviewed from 01/01/2012 to 08/1/2016. A list of MICU patients will be generated by the corresponding ICD-9 and ICD-10 codes for septic shock. Patients will be stratified into 4 groups: 1) not on either a chronic β -blocker or ACE-Inhibitor, 2) on chronic β -blocker, 3) on chronic ACE-Inhibitor, and 4) on both chronic β -blocker and ACE-inhibitor.

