5. METHODS AND STUDY PROCEDURES

5.1. Efficacy & Safety Assessments

The electronic medical record system (EPIC) will be used to collect data, including: patient age, gender, weight, height, BMI, race, past medical history (hypertension, diabetes, heart failure, afib/flutter, arrhythmia, history of myocardial infarction, history of CVA, CAD, CKD, dyslipidemia, asthma, COPD, cancer), Charlson Comorbidity Index, hospital length of stay, medical intensive care unit (MICU) length of stay. Prior to admission medications include: beta-blockers, ACE-inhibitors, amlodipine, diltiazem, ARBs, hydralazine, clonidine, hctz, loop diuretics, amiodarone, other antiarrhythmics. Vasopressor types and cumulative doses including: norepinephrine, epinephrine, phenylephrine, dopamine, and vasopressin. Epinephrine, phenylephrine, and dopamine will be converted to norepinephrine equivalents in concordance with other literature: 100 mcg dopamine equivalent to 1 mcg norepinephrine, 1 mcg epinephrine equivalent to 1 mcg norepinephrine, and 2.2 mcg phenylephrine equivalent to 1 mcg norepinephrine.^{5,6} Concomitant medications including: hydrocortisone, inotrope use, crystalloid type and amount, colloid use, albumin use, timing of antibiotics, and sedation choice if given. Clinical information collected include: Peak lactate, MAP, mechanical ventilation, in hospital mortality, 28 and 90 day mortality if available. SOFA score will be calculated as a measure of disease severity.

Study Timeline:

Date	Activity
September 2016	Rush University Medical Center IRB approval
October - November 2016	Data collection
December 2016	Data analysis
January 2017	Study presentation and manuscript preparation

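### Entry is conditional on vasopressor treatment, which follows the home exposure and starts the outcome, so the unadjusted comparison supports an association among recipients but not the stated effect on dose

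*Combined protocol and SAP*

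**What the plan says.** **Entry.** The disease criterion in Section 3.2 is "Diagnosis of septic shock requiring vasopressor therapy (norepinephrine, epinephrine, phenylephrine, dopamine, or vasopressin". Section 4.1 applies it at screening: "Adult patients 18 years of age or older with septic shock who received treatment with a vasopressor will be assessed for inclusion". Neither section gives a blood pressure, lactate or prior-fluid criterion that would hold the entry threshold equal across cohorts.

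**Objective and hypothesis.** Section 1.2 sets out to "determine the effect of chronic β -blocker or ACE-inhibitor on cumulative vasopressor dosing in the first 48 hours of septic shock". Section 1.1 is worded more cautiously and expects use of the drugs to be "associated with decreased cumulative doses of vasopressors administered in the first 48 hours of septic shock".

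**Severity data.** Section 5.1 states: "Clinical information collected include: Peak lactate, MAP, mechanical ventilation". It adds that "SOFA score will be calculated as a measure of disease severity". No time point is given for SOFA or MAP, and lactate is named only as the peak.

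**Analysis.** Section 13.2 plans a fixed-effects ANOVA across the four cohorts for 48-hour cumulative dose, with post hoc pairwise comparisons. It names no covariate, matching, restriction or sensitivity analysis. Section 2.2 says little is known about how these drugs bear on vasopressor dosing and shock severity, but it does not discuss selection at entry.

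**The concern.** The sample is formed by an event that lies between exposure and outcome. Suppose a home antihypertensive lowers the severity of sepsis at which a patient comes to need a vasopressor. Mildly septic users then enter cohorts 2 to 4, while equally septic non-users never receive a vasopressor and are missing from cohort 1. Mean severity at entry is lower in users, and so is mean dose, even if the drug does nothing to dose.

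This is not ordinary confounding by comorbidity. Adjusting for the Charlson index would not deal with it, because the imbalance is in acute severity at entry. What is at stake is the interpretation: a lower mean dose in users could be reported as an effect of the drugs when part or all of it comes from who was admitted to the sample.

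**Working it through.** **1. The plan's own figure.** One-way ANOVA, four groups, f = 0.25, α = 0.05: at N = 180, λ = 180 × 0.25² = 11.25, critical F = 2.656 and power = 0.804, as Section 13.1 states. At the target of N = 200, power is 0.848.

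**2. What f = 0.25 means here.** If one cohort differs from three equal cohorts by d SDs, then f = d√3/4. The plan's 50/25/25/25 mg with SD 10 gives d = 2.5 and f = 2.5 × 0.433 = 1.0825, matching its output. For f = 0.25, d = 4 × 0.25/√3 = 0.58.

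**3. Selection model (all inputs assumed; the documents give none).** Severity S is standard normal in septic patients. Non-users enter if S > c, with c = 0.5, 1.0 or 1.5. Users enter if S > c − b, with b = 0.1 to 0.5. The drugs do not alter dose at a given severity. Mean severity of entrants is m(c) = φ(c)/[1 − Φ(c)], with variance 1 + c·m − m².

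Worked case, c = 1.0 and b = 0.5:
- Non-users: 0.2420/0.1587 = 1.525. Users: 0.3521/0.3085 = 1.141. Gap = 0.384.
- Variance in non-user entrants: 1 + 1.525 − 2.326 = 0.199, so SD = 0.446.
- (A) Correlation 0.5 among entrants: 0.5 × 0.384/0.446 = 0.43 SD of dose.
- (B) Correlation 0.5 in all septic patients: dose SD among entrants = √(0.25 × 0.199 + 0.75) = 0.894, so 0.5 × 0.384/0.894 = 0.21 SD.

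| c | b | severity gap | (A) | (B) |
|---|---|---|---|---|
| 0.5 | 0.1 | 0.072 | 0.07 | 0.04 |
| 0.5 | 0.5 | 0.343 | 0.33 | 0.19 |
| 1.0 | 0.1 | 0.079 | 0.09 | 0.04 |
| 1.0 | 0.5 | 0.384 | 0.43 | 0.21 |
| 1.5 | 0.1 | 0.085 | 0.11 | 0.05 |
| 1.5 | 0.5 | 0.414 | 0.53 | 0.23 |

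Differences are in dose SDs of non-user entrants. The range is 0.07 to 0.53 on basis A and 0.04 to 0.23 on basis B.

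**4. Chance of a significant ANOVA at N = 200 with no drug effect on dose.** Use f = d√3/4 and λ = 200f². For d = 0.23, f = 0.100 and λ = 1.98, giving 19%. For d = 0.53, f = 0.229 and λ = 10.5, giving 78%. At the low ends (0.04 and 0.07) it is 5% and 6%, close to nominal.

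**5. Direction.** If a share a of the threshold shift also raises dose at equal severity, the net difference in severity units is −gap + a·b, which is zero at a = gap/b. In the worked case a = 0.384/0.5 = 0.77, and with full carry-through users are higher by 0.5 − 0.384 = 0.116. With thresholds that 10% to 50% of non-users cross, reversal occurs at a = 0.58 to 0.83.

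**6. Would restricting to raised lactate solve it?** Simulated at c = 1.0, b = 0.25 and 0.5, lactate-severity correlation 0.3 to 0.7 and cut-offs of 0 to 1.5 SD (all assumed), 57% to 96% of the severity gap remains. For example, with b = 0.5, correlation 0.5 and cut-off 1.0, the gap falls only from 0.384 to 0.318 (83% remains).

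**The case against.** **The question concerns patients in shock.** Dose in the first 48 hours of septic shock is naturally studied in those who receive a vasopressor, Section 1.1 already speaks of association, and the design is openly a retrospective cohort. That stands, and it is why the remedy is mainly one of wording. It does not rescue the claim of an effect in Section 1.2.

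**The mechanism is assumed.** Nothing in the documents shows that home antihypertensives lower the threshold for vasopressors, and a shift of 0.1 SD would matter little. A drug that brings on hypotension may also raise the dose needed at equal severity, which would work against the hypothesis. This stands in full. A reader might infer that selection explains, or is bound to favour, the hypothesised lower dose; the documents support neither.

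**SOFA is collected.** A reader might infer from the peak-only lactate that the data set holds no usable marker of severity at entry. Section 5.1 does not support that: SOFA is planned and would allow partial adjustment. The gap is narrower: no time point is fixed, and Section 13.2 gives the score no role.

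**Conclusion.** The point holds as a structural limit on interpretation, of unknown size and direction. Entry depends on an event that follows the exposure and begins the outcome, and no part of the plan addresses this. Under the stated assumptions the spurious difference runs from negligible (0.04 SD) to nearly the size the study is powered for (0.53 against 0.58 SD). The upper end requires a 0.5 SD shift, a high threshold and a 0.5 correlation that holds among patients already selected. If that correlation holds across all septic patients, the ceiling is 0.23 SD. Every figure also assumes no drug effect on dose at equal severity; relaxing that can shrink or reverse the difference.

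It would also go too far to infer that agreement between the main result and a lactate-restricted one clears the way to claim lower dosing. Both are drawn from vasopressor recipients and keep most of the severity gap, so they would tend to agree even when both are biased. The study remains sound as a description of association among recipients.

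**What to change.** 1. In Section 1.2, replace *effect* with *association among patients given vasopressors*, limit the conclusion to that, and bring it into line with Section 1.1.
2. In Section 5.1, score SOFA from the last values before vasopressor start, with and without its cardiovascular component, since blood-pressure drugs could move that component directly. Record the first lactate at or before that time in addition to the peak.
3. In Section 13.2, pre-specify a sensitivity analysis of 48-hour cumulative dose adjusted for these measures and report it beside the ANOVA. State that it removes selection only as far as the measures capture severity at entry, and that agreement with the ANOVA does not establish an effect. Do not make agreement with a lactate-restricted analysis a condition that licenses a claim of lower dosing.

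Cost: a little more chart abstraction from records already being reviewed, one further analysis, and a more modest claim.

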4. SUBJECT IDENTIFICATION, RECRUITMENT AND CONSENT

4.1. Method Of Subject Identification And Recruitment

The study will be retrospective, and collected data will be a result of routine care. Adult patients 18 years of age or older with septic shock who received treatment with a vasopressor will be assessed for inclusion. Patients will be excluded if they are pregnant, transferred from outside hospital on vasopressor, admitted in cardiopulmonary arrest, prior arrest within 24 hours of admission to RUMC or if they required neuromuscular blockade.

Patients will be reviewed from 01/01/2012 to 08/1/2016. A list of MICU patients will be generated by the corresponding ICD-9 and ICD-10 codes for septic shock. Patients will be stratified into 4 groups: 1) not on either a chronic β -blocker or ACE-Inhibitor, 2) on chronic β -blocker, 3) on chronic ACE-Inhibitor, and 4) on both chronic β -blocker and ACE-inhibitor.

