13. DATA ANALYSIS AND MONITORING

13.1. Sample Size Determination

There are limited data for proper evaluation of a sample size. However, there was a smaller presented study that had a dramatic decrease in norepinephrine dose in patients on a β -blockers or ACE-inhibitors prior to admission for patients in circulatory shock of any kind.⁷ Using these data, estimated 48h cumulative mean dose for norepinephrine patients not on anti-hypertensives will be 50 mg (SD = 10) and estimated 48h cumulative mean dose for norepinephrine for beta blocker, ACE-Inhibitor, and beta-blocker + ACE-Inhibitor groups will be 25 mg (SD = 10). Using a 4-way fixed effects ANOVA power calculation with estimated effect size from previous study ($f = 1.08$) the total sample size would be 16

F tests – ANOVA: Fixed effects, omnibus, one-way

Analysis: A priori: Compute required sample size

Input: Effect size f	= 1.0825318
α err prob	= 0.05
Power (1- β err prob)	= 0.95
Number of groups	= 4
Output: Noncentrality parameter λ	= 23.4375020
Critical F	= 3.2388715
Numerator df	= 3
Denominator df	= 16
Total sample size	= 20
Actual power	= 0.9609969

However, the current proposed study is specifically looking at septic shock and the anticipated effect is unknown. Therefore, using a 4-way fixed effects ANOVA power calculation with a medium effect ($f = 0.25$) has a total sample size of 180 patients.

F tests – ANOVA: Fixed effects, omnibus, one-way

Analysis: A priori: Compute required sample size

Input: Effect size f	= 0.25
α err prob	= 0.05
Power (1- β err prob)	= 0.80
Number of groups	= 4
Output: Noncentrality parameter λ	= 11.2500000
Critical F	= 2.6559389
Numerator df	= 3

Denominator df	= 176
Total sample size	= 180
Actual power	= 0.8039869

A list of ICU patients will be generated by the corresponding ICD-9 and ICD-10 codes for septic shock during the inclusion time frame, randomized and screened until reaching the minimum power and equal groups (n = 200, 50 patients in each group)

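### Sections 3.2 and 4.1 give different exclusion lists, and the extra criterion in 4.1, neuromuscular blockade, has no definition or time window, so it can be met while the primary outcome is accruing

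*Combined protocol and SAP*

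**What the plan says.** The formal eligibility list is in section 3.2. It has four exclusions: pregnancy, "Transfer from outside hospital on vasopressors", "Admitted in cardiopulmonary arrest" and "Prior arrest within 24 hours of admission to RUMC".

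Section 4.1 describes how patients are identified. It states the same four exclusions and then a fifth, in the words "prior arrest within 24 hours of admission to RUMC or if they required neuromuscular blockade".

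The primary objective in section 1.2 concerns "cumulative vasopressor dosing in the first 48 hours of septic shock". Section 13.2 analyses that 48-hour dose with a fixed-effects ANOVA across the four cohorts and names no adjustment for severity. Section 5.1 lists the concomitant treatments to be extracted, among them hydrocortisone, inotropes, fluids, antibiotic timing and choice of sedation. Neuromuscular blockade is not named there.

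**The concern.** There are two linked problems.

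The first is consistency. A screener working from 3.2 keeps a patient who received blockade; one working from 4.1 removes that patient. Both texts are current, and nothing in the document says which governs.

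The second is timing. The study is retrospective, so the whole hospital course is visible when a chart is screened. An exclusion with no time limit can be triggered by treatment given after the exposure (chronic therapy before admission) and during the period in which the outcome is measured. That is selection on a post-exposure event. If patients who receive blockade tend to be sicker or need more vasopressor, and if this differs between cohorts, the comparison of mean doses changes for reasons unrelated to the study question. An analysis by cohort alone would not correct for it. Unless blockade is recorded, nobody could later tell how many patients were removed, from which cohorts, or when.

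**Working it through.** The check is a comparison of texts; the plan gives no figure on this point to reproduce.

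**Step 1: the two lists side by side.**

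| Exclusion | Section 3.2 | Section 4.1 | Time anchor in the wording |
|---|---|---|---|
| Pregnancy | yes | yes | none, but a patient characteristic rather than a treatment |
| Transfer while on vasopressors | yes | yes | at or before arrival |
| Arrest at admission | yes | yes | admission |
| Earlier arrest | yes | yes | 24 hours of admission |
| Neuromuscular blockade | **no** | **yes** | **none** |

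Four criteria match and one does not. Three of the four shared criteria are tied by their wording to admission or earlier; the unmatched one is not tied to any time.

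**Step 2: look for a definition elsewhere.** The phrase in 4.1 is the only mention of blockade in the document. No agent, indication, duration (a single dose as against an infusion, for example) or window is given. Section 6 treats disallowed medications as not applicable to this design, which neither defines the criterion nor resolves the difference.

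**Step 3: who is eligible under each reading.** Let time zero be the start of the 48-hour outcome window.

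| First blockade | 3.2 alone | 4.1 as written | Limited to before time zero |
|---|---|---|---|
| Before time zero | eligible | excluded | excluded |
| Within the 48 hours | eligible | excluded | eligible |
| After the 48 hours | eligible | excluded | eligible |
| Never | eligible | eligible | eligible |

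The second and third rows are the difficulty: under 4.1 as written, what happens after time zero decides who is analysed. Section 1.2 counts hours of septic shock but does not say which recorded event starts the clock, so time zero must be stated before any limit can be applied.

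**Step 4: what the choice of list does to the estimate.** For cohort *i*, let *m_i* be the mean 48-hour dose in patients without blockade, *p_i* the share who received it, and *d_i* the mean dose of blocked minus unblocked patients.

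- Mean under 3.2: *m_i + p_i d_i*
- Mean under 4.1: *m_i*
- Change in the cohort 1 minus cohort 2 difference on moving from 3.2 to 4.1: (*m_1 − m_2*) − [(*m_1 + p_1 d_1*) − (*m_2 + p_2 d_2*)] = *p_2 d_2 − p_1 d_1*

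The change is zero when the two products are equal and can otherwise take either sign. The documents give no value of *p* or *d* for any cohort, so no figure in mg follows from them.

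**The case against.** The strongest reply is that 4.1 contains everything in 3.2. Section 3.2 omits blockade; it does not say that blocked patients are eligible. A screener who applies the whole protocol would use all five criteria and reach a single population. This is fair, and it reduces the conflict to an omission from one list. It does not remove the conflict, because 3.2 is the section headed as the eligibility criteria and a reader may reasonably rely on it alone. Nor does it address timing, since the unbounded criterion is in 4.1 itself.

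A second reply is that the bias is hypothetical. That also stands. No section links blockade to severity, dose or cohort, and none says that blockade will be assessed during the 48 hours. The wording permits it; it does not require it.

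A third is that the data items in 5.1 are introduced as inclusions, so the absence of blockade does not prove that it will go unrecorded. Agreed: it shows only that the plan does not commit to recording it.

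A reader might go further and infer that the criterion will bias the primary result, perhaps towards a smaller difference between cohorts. The documents do not support this. Step 4 shows that the change can be zero or of either sign, and any direction would have to come from assumptions made outside the plan.

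**Conclusion.** The point holds as an internal inconsistency combined with a missing time limit. It is certain that the two lists differ, that the criterion is undefined, and that its wording allows a patient to be excluded for care given after shock onset. It is not established that the comparison would be biased. That requires blockade to be related to severity or vasopressor dose in a way that makes *p_i d_i* differ between cohorts, which is an assumption. Size and direction cannot be derived from the documents.

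This should be corrected before screening, because it decides who enters the primary analysis and the correction is cheap. It does not by itself invalidate the design.

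**What to change.** Before screening begins, reconcile 3.2 and 4.1 into one exclusion list in one of two ways:

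- without the blockade criterion; or
- with it in both sections, defined, and limited to events before the start of the 48-hour outcome window, with that time zero stated.

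The choice belongs to the investigators. What matters for the analysis is that nothing occurring after time zero decides eligibility.

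Under either option, add blockade use and start time to the section 5.1 data items for patients who meet all other criteria, and report the number affected by cohort. If any patients are excluded on this ground, collect their 48-hour dose and repeat the primary analysis with them included. If the criterion is dropped, a repeat analysis that removes everyone who received blockade is not advised, because it would bring back the same post-exposure selection.

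The cost is a wording change, one chart field, dose extraction for any patients excluded on this ground, and one extra analysis.
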